5.5 IRB Re-Approval

Annual IRB re-approval from the Participating institution is required in order to register participants onto a protocol. There is no grace period for annual re-approvals.

Protocol registrations will not be completed if a re-approval letter is not received by the DF/HCC Lead Institution or designee from the Participating Institutions on or before the anniversary of the previous approval date.

5.6 Participant Confidentiality and Authorization Statement

The Health Insurance Portability and Accountability Act of 1996 contains, as one of its six major components, the requirement to create privacy standards for health care information that is used or disclosed in the course of treatment, payment or health care operations. The original Privacy Rule, as it has come to be known, was published in December 2000. The Final Rule was published on August 14, 2002, which has modified the privacy rule in significant ways vis-à-vis research.

In order for covered entities to use or disclose protected health information during the course of a DF/HCC Multi-Center Protocol the study participant must sign an Authorization. This Authorization may or may not be separate from the Informed Consent. The DF/HCC Multi-Center Protocol, with the approval from the DFCI IRB and if applicable NCI/CTEP, will provide an Informed Consent template, which covered entities (DF/HCC Multi-Center Protocol participating institutions) must use.

The DF/HCC Multi-Center Protocol will use all efforts to limit its use of protected health information in its trials. However, because of the nature of these trials, certain protected health information must be collected per National Cancer Institute requirements. These are the primary reasons why DF/HCC has chosen to use Authorizations, signed by the participant in the trial, rather than limited data sets with data use agreements.

5.7 Participant Registration

To register a participant, the following documents should be completed by the DF/HCC Multi-

Center Protocol participating site and faxed to the Lead Institution's study coordinator at [contact]. :

- Copy of required laboratory tests [Hematology, Chemistry, Lipid Panel and Secretary Proteins]
- Signed informed consent form
- HIPAA authorization form (if separate from the informed consent document)
- Other appropriate forms including the Eligibility Screening Worksheet, and Pathology Report confirming diagnosis,)

The research DF/HCC Multi-center Protocol participating site will then call or e-mail the Lead Institution or designee to verify eligibility. To complete the registration process, the Lead Institution or designee will:

- Register the participant on the study with the DF/HCC Quality Assurance Office for Clinical Trials (QACT)
- Fax or e-mail the participant case number, and if applicable the dose treatment level, to the participating site
- Call the research nurse or data manager at the participating site and verbally confirm registration

5.8 DF/HCC Multi-center Protocol Case Number

Once eligibility has been established and the participant successfully registered, the participant is assigned a five digit protocol case number. This number is unique to the participant on this trial and must be used for QACT CRF/eCRF completion and written on all data and QACT correspondence for the participant.

5.9 DF/HCC Multi-center Protocol Registration Policy

5.9.1 Initiation of Therapy: Participants must be registered with the DF/HCC QACT before receiving treatment. Treatment may not be initiated until the site receives a faxed or e-mailed copy of the participant's Registration Confirmation memo from the DF/HCC QACT. Therapy must be initiated per protocol guidelines. The Protocol Chair and DFCI IRB must be notified of any exceptions to this policy.

5.9.2 Eligibility Exceptions: The DF/HCC QACT will make no exceptions to the eligibility requirements for a protocol without DFCI IRB approval. The DF/HCC QACT requires each institution to fully comply with this requirement.

5.9.3 Verification of Registration, Dose Levels, and Arm Designation: A registration confirmation memo for participants registered to DF/HCC Multi-Center Protocol will be faxed or emailed to the registering institution within one working day of the registration. Treatment may not be initiated until the site receives a faxed or e-mailed copy of the registration confirmation memo.

5.9.4 Confidentiality: All documents, investigative reports, or information relating to the participant are strictly confidential. Any participant specific reports (i.e. Pathology

Reports, MRI Reports, Operative Reports, etc.) submitted to the Lead Institution or designee must have the participant's full name & social security number "blacked out" and the assigned DF/HCC QACT case number and protocol number written in (with the exception of the signed informed consent document). Participant initials may only be included or retained for cross verification of identification.

5.10 Schedule of Data Submission

The DF/HCC QACT develops a set of either paper or electronic case report forms, (CRF/eCRFs) for use with the DF/HCC Multi-Center Protocol. These forms are designed to collect data for each study. The schedule for submission of case report forms to the DF/HCC QACT is generally specified in each protocol. When not specified in the protocol, the DF/HCC QACT will require the forms to be submitted as follows:

COMMON FORMS & REPORTS

- Eligibility Checklist, (Informed Consent/ Participant Authorization for the Release of Personal Health Information)
- On-study Form
- Baseline Assessment Form (Baseline disease assessment/measurement)
- Treatment Forms
- Adverse Event Forms
- Response Assessment Form (Follow-up disease assessment/Measurement)
- Off-Treatment/Off Study Form
- Follow-Up/Survival Forms

Note: It is necessary to send only ONE copy of all paper Case Report Forms.

Please see section 12.1.2 of the protocol for schedule of data submission.

5.10.1 Eligibility Checklist

Purpose - Outlines protocol-specific eligibility criteria and includes the following:

Participant Demographics (address, zip code, sex, race, ethnicity, initials, date of birth)

- 1) Parameters for eligibility
- 2) Parameters for exclusion
- 3) Parameters for stratifications

If a time frame is not specified in the protocol, tests must be completed as follows:

- Lab tests required for eligibility must be completed within 14 days prior to study enrollment by the QACT.
- For protocols requiring measurable disease, lab baseline measurements must be completed within 28 days prior to study enrollment by the QACT. Examples: tumor markers and hormones (Chromogranin A, Gastrin, VIP).
- Non-lab tests required for eligibility must be performed within 28 days prior to study entry. Example: radiological scans
-

- **Schedule for Submission** - Completed prior to participant registration. The Informed Consent/ Participant Authorization for the Release of Personal Health Information should be submitted with the Eligibility Checklist at the time of registration.

5.10.2 On-study Form

Purpose - documents the following items:

- Demographic data
- Prior therapy
- Past medical and surgical history
- Description of participant's physical status at protocol registration
- Disease site specific data

5.10.3 Baseline Assessment Form

Purpose – Documents objective and subjective disease status as defined by the protocol. Records all pertinent radiographic and laboratory measurements of disease utilized in determining response evaluations.

5.10.4 Treatment Form

Purpose - Records the following information related to the time the participant receives protocol treatment:

- Participant, Protocol, Affiliate information
- Protocol treatment and supportive therapy per treatment cycle
- Protocol specific laboratory values per treatment cycle
- All medications other than protocol chemotherapy agents used to treat concomitant diagnoses, if applicable

5.10.5 Adverse Event Report Form

Purpose – Documents adverse events that occur while the participant is receiving treatment and for up to 30 days after the last dose of treatment. All adverse events are to be graded by number using the toxicity grading scale required by the protocol. *This form is not for IRB submission, but for recording the AE in the research database.*

5.10.6 Response Assessment Form

Purpose – Documents objective and subjective response as defined by the protocol. Records all pertinent radiographic and laboratory measurements of disease utilized in

determining response evaluations.

5.10.7 Off Treatment/Off Study Form

Purpose - The Off Treatment/Off Study Form is submitted when the participant is removed from the study or has completed all protocol treatment. Note: If the participant dies while on protocol, the Off Study Form is the last form submitted.

5.10.8 Follow up / Survival Form

Purpose - Summarizes participant status at a given point in time after being removed from treatment.

5.11 Data Form Review

When data forms arrive at the DF/HCC QACT, they are reviewed for:

Timeliness:

Did the form arrive on time as specified in the protocol?

Completeness:

Is all the information provided as required per protocol?

Participant Eligibility:

Does the participant meet the eligibility requirements for the study based on the demographic data, lab values and measurements provided?

Stratification:

Are the stratification parameters consistent with what was given at the time of registration?

Protocol Treatment Compliance:

Are the body surface area (BSA) and drug dosage calculations correct? The dose must be within 10% of the calculated protocol dose.

Adverse Events (Toxicities):

Did the participant experience adverse events (toxicities or side effects) associated with the treatment? Was the treatment delayed due to the adverse event? What was the most severe degree of toxicity experienced by the participant?

Notations concerning adverse events will address relationship to protocol treatment for each adverse event grade. All adverse events encountered during the study will be evaluated according to the NCI Common Toxicity Criteria assigned to the protocol and all adverse events

must be noted on the participant's Adverse Event (Toxicity) Forms.

Response:

Did the participant achieve a response? What level of response did they achieve? On what date did the participant achieve the response and how was the response determined?

Response criteria are defined in the protocol. A tumor assessment must be performed prior to the start of treatment and while the participant is on treatment as specified by the protocol.

Objective responses must have documentation such as physical measurements, x-rays, scans, or laboratory tests.

A subjective response is one that is perceived by the participant, such as reduction in pain, or improved appetite.

5.12 Missing and Deficient Memorandum

Data submissions are monitored for timeliness and completeness of submission. Participating institutions are notified of their data submission delinquencies in accordance with the following policies and procedures:

Incomplete or Questionable Data

If study forms are received with missing or questionable data, the submitting institution will receive a written query from the DF/HCC QACT Data Analyst. Responses to the query should be completed and returned within 14 days. Responses may be returned on the written query or on an amended case report form. In both instances the query must be attached to the specific data being re-submitted in response.

Missing Forms

If study forms are not submitted on schedule, the participating institution will receive a Missing Form Report from the DF/HCC QACT noting the missing forms. These reports are compiled by the DF/HCC QACT and distributed a minimum of three times a year.

6.0 REQUISITIONING INVESTIGATIONAL DRUG

The ordering of investigational agent is generally specified in the protocol.

Participating sites will be supplied the investigational agents by the DF/HCC Lead Institution. Participating sites will contact Lead Institutions Research Pharmacy by email or phone and drugs will be shipped overnight via FedEx to the shipment address provided by participating sites. Drug should be stored as specified in section 4.5 of the protocol. It is the responsibility of the Participating sites to contact Lead Institutions Research Pharmacy. A log should be kept of all investigational drug dispensed on the NCI drug accountability forms.

The local IRB should be kept informed of who will supply the agent (i.e., NCI or a pharmaceutical company) so that any regulatory responsibilities can be met in a timely fashion.

7.0 SAFETY ASSESSMENTS AND TOXICITY MONITORING

All participants receiving investigational agents will be evaluated for safety. The safety parameters include all laboratory tests and hematological abnormalities, physical examination findings, and spontaneous reports of adverse events reported to the investigator by participants.

All toxicities encountered during the study will be evaluated according to the NCI criteria assigned to the protocol (CTCAE Version 3.0) and recorded prior to each course of therapy. Life-threatening toxicities should be reported immediately to the Protocol Chair and Institutional Review Board (IRB).

Additional safety assessments and toxicity monitoring will be outlined in the protocol.

7.1 Serious Adverse Events

A serious adverse event (SAE) is any adverse drug experience at any dose that results in any of the following outcomes: death, a life-threatening adverse drug experience, inpatient hospitalization or prolongation of existing hospitalization, a persistent or significant disability/incapacity, or a congenital anomaly/birth defect. Important medical events that may not result in death, be life-threatening, or require hospitalization may be considered serious when, based upon appropriate medical judgment, they may jeopardize the participant or may require medical or surgical intervention to prevent one of the outcomes listed in this definition. Examples of such medical events include allergic bronchospasm requiring intensive treatment in an emergency room or at home, blood dyscrasias or convulsions in a participant who has never had seizure activity in the past that do not result in inpatient hospitalization, or the development of drug dependency or abuse.

Unless otherwise specified in the protocol, the study will utilize the Cancer Therapy Evaluation Program (CTEP) Common Terminology Criteria for Adverse Events (CTCAE) Version 3.0 for Toxicity and Adverse Event reporting. A copy of the CTC or CTCAE Criteria can be downloaded from the CTEP home page (<http://ctep.info.nih.gov>).

7.2 Guidelines for Reporting Serious Adverse Events

Guidelines for reporting Serious Adverse Events (SAEs) will be followed as is delineated in the protocol.

In addition, the Participating Institutions must report the serious adverse events to the Protocol Chair and the Coordinating Center (Lead Institution) at the time SAEs are submitted.

The Lead Institution will maintain documentation of all Adverse Event Reporting and be responsible for communicating all SAEs to all Participating sites.

7.3 Guidelines for Processing IND Safety Reports

The U.S. Food and Drug Administration (FDA) regulations require sponsors of clinical studies to notify the FDA and all participating investigators of any serious and unexpected adverse experiences that are possibly related to the investigational agent.

IND Safety Reports: The Protocol chair at the Lead Institution. will be sent a copy of expedited adverse events reports.. Within 7 business days of receipt of the notification, the Lead Institution or designee will forward the letters by email to the Participating sites with protocol specific instructions for IRB submissions, participant notifications, etc. For routine IND Safety Reports, that do not require an immediate revision to the protocol and/or model informed consent documents should be filed with their protocol and a copy of the report sent to their IRB according to their local IRB's policies and procedures.

8.0 PROTOCOL VIOLATIONS AND DEVIATIONS

Neither the FDA nor the ICH GCP guidelines define the terms “protocol violation” or “protocol deviation.” All DF/HCC Protocol Chairs must adhere to those policies set by the DFCI IRB, the definitions for protocol violation and deviation as described by the DFCI IRB will be applied for reporting purposes for all institutions participating in the DF/HCC Multi-center Protocol.

8.1 Definitions

Protocol Deviation: Any departure from the defined procedures set forth in the IRB-approved protocol.

Protocol Violation: Any protocol deviation that was not prospectively approved by the IRB prior to its initiation or implementation.

8.2 Reporting Procedures

The Protocol Chair: is responsible for ensuring that clear documentation is available in the medical record to describe all protocol deviations and violations. The Protocol Chair will also be responsible for ensuring that all protocol violations/deviations are promptly reported per DFCI IRB guidelines.

Participating Institutions: Protocol deviations require prospective approval from DFCI IRB. The Participating institution must submit the deviation request to the Protocol Chair and Lead Institution or designee, who will submit the deviation request to the DFCI IRB. Upon DFCI IRB approval the deviation should be submitted to the participating site's own IRB, per its policy. Protocol violations occurring at a participating institution will be submitted to that site's own IRB. A copy of the participating institution's IRB report and determination will be forwarded to the DF/HCC Lead Institution or designee by facsimile, within 10 business days after the original submission.

Coordinating Center: Upon receipt of the violation/deviation report from the participating

institution, the DF/HCC Lead Institution or designee will submit the report to the Protocol Chair for review. Subsequently, the participating institution's IRB violation/deviation report will be submitted to the DFCI IRB for review per DFCI IRB reporting guidelines.

9.0 QUALITY ASSURANCE

- 1) The quality assurance process for a clinical trial research study requires verification of protocol compliance and data accuracy. As the Coordinating Center, the DF/HCC Lead Institution or designee with the aid of the QACT provides quality assurance oversight for the DF/HCC Multi-center Protocol.

9.1 Ongoing Monitoring of Protocol Compliance

All data submitted to the DF/HCC QACT will be monitored for timeliness of submission, completeness, and adherence to protocol requirements. Monitoring will begin at the time of participant registration and will continue during protocol performance and completion. The Lead Institution or designee and if applicable QACT Data Analysts assigned to the Protocol will perform the ongoing protocol compliance monitoring with the support of the participating institution's Coordinators, the Principal Investigators, and the Protocol Chair.

9.2 Evaluation of Participating Institution Performance

9.2.1 Eligibility Checklist: Eligibility criteria are checked on a protocol-specific eligibility checklist and faxed to the DF/HCC QACT prior to registration on protocol. The checklist and informed consent document are reviewed by a DF/HCC QACT Protocol Registrar before the participant can be registered on a protocol. The DF/HCC QACT cannot make exceptions to the eligibility requirements.

9.2.5 Accrual of Eligible Participants: Annual accrual rates for eligible participants enrolled onto therapeutic clinical trials is calculated for each institution. Institutions are expected to maintain the minimum annual average accrual as defined by the protocol grant or contract.

9.3 On-Site Auditing

9.3.1 DF/HCC Sponsored Trials

For all DF/HCC sponsored protocols:

The participating institutions are required to submit subject source documents to the DF/HCC Lead Institution or designee for monitoring. Participating sites will be asked to submit material for the first patient after completion of 2 cycles. Thereafter, subjects will be selected at random for on-site monitoring conducted by the DF/HCC Lead Institution or designee. Participating sites will be notified 28 days prior to monitoring visit.

DF/HCC Lead Institution requires the participating site to submit all relevant source documentation after the first patient is enrolled and has completed their 1st restaging scan.

9.3.2 Participating Institution

It is the participating institution's responsibility to notify the DF/HCC Lead Institution or designee of all scheduled audit dates and re-audit dates (if applicable), which involve the DF/HCC Multi-Center Protocol. All institutions will forward a copy of final audit and/or re-audit reports and corrective action plans (if applicable) to the DF/HCC Lead Institution or designee within 12 weeks after the audit date.

9.3.3 Coordinating Center (Lead Institution or designee)

The Protocol Chair will review all DF/HCC Multi-Center Protocol Final Audit reports and corrective action plans if applicable. The Lead Institution or designee must forward these reports to the DF/HCC QACT per DF/HCC policy for review by the DF/HCC Audit Committee. Based upon the audit assessments the DF/HCC Audit Committee could accept or conditionally accept the audit rating and final report. Conditional approval could require the Protocol Chair to implement recommendations or require further follow-up. For unacceptable audits, the Audit Committee would forward the final audit report and corrective action plan to the DFCI IRB as applicable.

9.4 Sub-Standard Performance

The Protocol Chair, DFCI IRB and the NCI for CTEP trials, is charged with considering the totality of an institution's performance in considering institutional participation in the DF/HCC Multi-Center Protocol.

9.4.1 Corrective Actions: Institutions that fail to meet the performance goals of accrual, submission of timely accurate data, and adherence to protocol requirements will be recommended for a six-month probation period. Such institutions must respond with a corrective action plan and must demonstrate during the probation period that deficiencies have been corrected, as evidenced by the improved performance measures. Institutions that fail to demonstrate significant improvement will be considered by the Protocol Chair for revocation of participation.

07-325 RAD001 and Temozolomide

Name: _____ **MRN:** _____
Cycle: _____
RAD001 Dose: _____

*RAD001 is to be taken every day, in the morning, on an empty stomach, 1 hour before breakfast
 You will not make up any missed or vomited doses of drug. Do resume your regular dose the next day.
 Bring your study drugs and this diary to clinic each visit.*

Day	Date	Drug	Dose	Time	Symptoms
1		RAD001		: AM	
2		RAD001		: AM	
3		RAD001		: AM	
4		RAD001		: AM	
5		RAD001		: AM	
6		RAD001		: AM	
7		RAD001		: AM	
8		RAD001		: AM	
9		RAD001		: AM	
10		RAD001		: AM	
11		RAD001		: AM	
12		RAD001		: AM	
13		RAD001		: AM	
14		RAD001		: AM	
15		RAD001		: AM	
16		RAD001		: AM	
17		RAD001		: AM	
18		RAD001		: AM	
19		RAD001		: AM	
20		RAD001		: AM	
21		RAD001		: AM	
22		RAD001		: AM	
23		RAD001		: AM	
24		RAD001		: AM	
25		RAD001		: AM	
26		RAD001		: AM	
27		RAD001		: AM	
28		RAD001		: AM	

Patient's Signature: _____ Date: _____

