4.4 Dose Modification

4.4.1 RAD001 dose adjustments

Three RAD001 dose levels are defined for dose adjustment: 10 mg daily, 5 mg daily, and 5 mg every other day.

Table 4.1.1 : Dose Reduction Schedule for RAD001 – Cohort 1

Dose Level	Dose and schedule	Days per cycle (cycle length = 28 days)
0	5 mg daily	Continuous
Decrease 1 dose level	5 mg every other day	Continuous
Decrease 2 dose levels	Discontinue therapy	

Table 4.1.2 : Dose Reduction Schedule for RAD001 – Cohort 2

Dose Level	Dose and schedule	Days per cycle (cycle length = 28 days)
0	10 mg daily	Continuous
Decrease 1 dose level	5 mg daily	Continuous
Decrease 2 dose levels	5 mg every other day	Continuous
Decrease 3 dose levels	Discontinue therapy	

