4.4.3 Dose reductions for hematologic toxicity

Cohort 1: If the ANC is $<1,000$ or the platelet count is $<50,000$ during study therapy, RAD001 and temozolomide will be delayed. If RAD001 or temozolomide cannot be administered on the scheduled day of dosing, the CBC will be repeated weekly for up to and including 3 weeks until the ANC is $\geq 1000/\text{mm}^3$ and the platelet count $\geq 50,000/\text{mm}^3$. At that time, temozolomide will be reinitiated at one reduced dose level ($100 \text{ mg}/\text{m}^2$ daily, see Tables 4.1-4.2). The dose of RAD001 will remain at 5 mg daily. For subsequent dose reductions, both temozolomide and RAD001 will be reduced by one dose level. If treatment is held more than 3 weeks, the patient should be taken off protocol therapy.

Cohort 2: If the ANC is $<1,000$ or the platelet count is $<50,000$ during study therapy, RAD001 and temozolomide will be delayed. If RAD001 or temozolomide cannot be administered on the scheduled day of dosing, the CBC will be repeated weekly for up to and including 3 weeks until the ANC is $\geq 1000/\text{mm}^3$ and the platelet count $\geq 50,000/\text{mm}^3$. At that time, RAD001 and temozolomide will be reinitiated at one reduced dose level (see Tables 4.1-4.2). If treatment is held more than 3 weeks, the patient should be taken off protocol therapy.

Growth factors cannot be used to induce elevations in neutrophil count for the purposes of administration of RAD001 and temozolomide on the scheduled dosing OR to allow treatment. Administration of erythropoietin is allowed.

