4.5 Treatment Plan

4.5.1 Investigational therapy

The investigational therapy used in the course of this study is RAD001 in combination with temozolomide. Study medication will be administered by the patients themselves. Patients are provided with a diary to document date, time, dose and any symptoms they experience while taking study medications. During the study, RAD001 will be administered orally as a once daily dose continuously from study day 1 until progression of disease or unacceptable toxicity. Patients in cohort 1 will receive RAD001 at a dose of 5 mg per day in combination with temozolomide 150 mg/m²/day on days 1-7 and 15-21 of each 28-day treatment cycle. Patients will be monitored for 7 days after their first cycle of therapy. They will not receive therapy during this observation period. Patients in cohort 2 will receive RAD001 at a dose of 10 mg per day in combination with temozolomide 150 mg/m²/day on days 1-7 and 15-21 of each 28-day treatment cycle. Patients will be monitored for 7 days after their first cycle of therapy. They will not receive therapy during this observation period. Patients in cohort 3 will receive RAD001 at the maximum tolerated dose in combination with temozolomide 150 mg/m²/day on days 1-7 and 15-21 of each 28-day treatment cycle.

Medication labels will comply with US legal requirements and be printed in English. They will supply no information about the patient. The storage conditions for study drug will be described on the medication label.

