4.5.4 Treatment compliance

Records of study medication used, dosages administered, and intervals between visits will be recorded during the study. Drug accountability will be noted and patients will be asked to return all unused study medication.

5 Visit schedule and assessments

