5.1.2 Evaluations during treatment

5.1.2.1 Day 1 of every cycle

- Physical examination
- Toxicity assessment
- Vital signs
- Weight
- Serum chemistries

- CBC with differential

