5.1.2.2 Day 15 of cycles 1 through 6 only

- Physical examination
- Toxicity assessment
- Vital signs
- Weight
- CBC with differential

5.1.2.3 Data to be obtained following every 2 cycles of treatment (time of restaging):

- Radiologic assessment of tumor burden by CT scan
- Assessment of serum chromogranin A and other secretory proteins (if applicable).

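### The RAD001 diary prints daily dosing for everyone, which contradicts the lowest dose level of 5 mg every other day and would double the dose of a patient who follows it

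*Combined protocol and SAP*

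**What the plan says.** Section 4.4.1 states: "Three RAD001 dose levels are defined for dose adjustment: 10 mg daily, 5 mg daily, and 5 mg every other day". In Table 4.1.1 (Cohort 1, starting at 5 mg daily) the every-other-day level is the first reduction. In Table 4.1.2 (Cohort 2, starting at 10 mg daily) it is the second. In both tables the next step is to stop therapy.

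Patients take the drug themselves, and Section 4.5.1 describes the form they use: "Patients are provided with a diary to document date, time, dose and any symptoms they experience while taking study medications". The RAD001 diary, printed at the end of the combined document after Appendix B, carries the fixed instruction "RAD001 is to be taken every day, in the morning, on an empty stomach, 1 hour before breakfast". For missed or vomited doses it adds: "Do resume your regular dose the next day". It names RAD001 on each of 28 daily rows. It has blanks for cycle and RAD001 dose and a dose cell for each day, but no field for schedule.

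On checking, Section 4.5.4 says "Drug accountability will be noted and patients will be asked to return all unused study medication". Routine treatment visits fall on "Day 1 of every cycle" (Section 5.1.2.1) and "Day 15 of cycles 1 through 6 only" (Section 5.1.2.2).

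**The concern.** The diary's only statement of frequency is wrong for one of the three dose levels that the protocol defines. The dose blank does not settle the matter. RAD001 comes as 5 mg tablets (Section 4.5.1.1), and the two lower levels differ only in how often one tablet is taken, so a dose entry of 5 mg reads the same for both.

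Patients reach the lowest level because of toxicity: hematologic (Section 4.4.3), non-hematologic (Section 4.4.4) or pneumonitis (Section 4.4.7). A patient who follows the form stays on the exposure that the reduction was meant to lower. The missed-dose line has the same fault: at this level the day after a missed dose is an off day.

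What is at stake is the safety of those patients and the fidelity of a dose reduction. The response endpoint and the two-stage rule are not affected.

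**Working it through.** The plan gives no cumulative RAD001 dose per cycle, so there is no figure of its own to reproduce. The check is direct arithmetic.

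**Inputs**
- Lowest level: 5 mg every other day (Section 4.4.1).
- Cycle length: 28 days (Tables 4.1.1 and 4.1.2).
- Diary frequency: daily, 28 rows.
- Routine visits: Days 1 and 15 in cycles 1 to 6, Day 1 only from cycle 7 (Sections 5.1.2.1 and 5.1.2.2). RAD001 has no fixed end and may run to progression (Section 4.1).

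**Formula:** dose over a period = mg per intake x number of intake days. Every-other-day dosing gives 14 intakes in 28 days, whether it starts on day 1 or day 2.

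| Period | Diary followed | Level assigned | Excess | Ratio |
|---|---|---|---|---|
| 28-day cycle | 28 x 5 = 140 mg | 14 x 5 = 70 mg | 70 mg | 2.0 |
| 14 days between visits, cycles 1 to 6 | 14 x 5 = 70 mg | 7 x 5 = 35 mg | 35 mg | 2.0 |
| 28 days between visits, cycle 7 on | 28 x 5 = 140 mg | 14 x 5 = 70 mg | 70 mg | 2.0 |

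For reference, 10 mg daily gives 28 x 10 = 280 mg per cycle. The 140 mg figure equals the 5 mg daily level, so following the form cancels the last reduction but exceeds no planned starting dose.

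**Who can be affected**
- From 10 mg daily: patients reduced twice.
- Cohort 1: patients whose RAD001 is reduced once. A first hematologic event there does not lower it (Section 4.4.3: "The dose of RAD001 will remain at 5 mg daily"), so on the hematologic route this means the second event. A non-hematologic reduction under Table 4.3 can lead there directly.

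The documents give no expected frequency for either route.

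**The case against.** The strongest reply is that the form is a record and not the dosing order. Its printed line matches the default regimen, and the every-other-day level is an exception directed by the investigator. Staff can write the schedule in the blank or strike rows by hand without any protocol change. The diary shown is headed for both drugs but lists only RAD001, so it may be one page of a set. Some pages ahead of Appendix B were not available for this review.

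There are also several safeguards:
- Section 4.3 requires at least weekly follow-up after an interruption for suspected drug toxicity, until resolution or grade 1.
- Section 4.4.3 requires weekly blood counts during a hematologic hold.
- Drug and diary are brought to each visit.
- A Treatment Form is due within 10 days of the end of the cycle (Section 12.1.2), and data review tests whether the dose is within 10% of the protocol dose (Appendix B, Section 5.11). A recorded doubling would fail that test.

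Much of this stands. Another diary version cannot be excluded, staff instruction may prevent the error, the doubling is conditional on the patient following the print, and this is a form-wording matter with no bearing on the analysis.

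It does not remove the contradiction. Nothing in the protocol tells staff to annotate the form, and a handwritten schedule would sit beside a printed line saying the opposite. Returns, diary review and the 10% test act after the doses are taken. For non-hematologic toxicity, weekly follow-up can end at grade 1, which is also when reduced dosing restarts (Section 4.4.4). After hematologic toxicity it may run past restart, because Section 4.4.3 allows restart on count thresholds and does not require grade 1.

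**Conclusion.** The concern holds. A fixed patient instruction contradicts a defined dose level, and following it at that level gives 140 mg instead of 70 mg per 28-day cycle. The excess before the next routine visit is at most 35 mg in cycles 1 to 6 and at most 70 mg from cycle 7 on.

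The size rests on three assumptions: the diary shown is the one used at the lowest level, the patient follows the printed line on every off day, and no contact outside the routine visits corrects the error. The number of patients at risk is unknown and may be small.

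No lasting misattribution of toxicity is claimed, because later diary and drug checks may uncover the error. The form should be corrected, since the protocol's last RAD001 level should not depend on the patient disregarding it.

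**What to change.** 1. Replace the fixed daily wording with a schedule field that site staff complete for each cycle: daily or every other day.
2. Have staff strike out the off-day rows before handing over the form whenever the every-other-day level is assigned.
3. Reword the missed-dose line so that the patient resumes on the next scheduled dosing day.

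The cost is one revised patient form and its IRB review. Design, endpoints and data collection do not change. If another diary version already covers the every-other-day level, it is enough for the protocol to name it and say when it replaces the standard page.
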